## Study Application (Version 1.0)

### 1.0 General Information

**\*Enter the full title of your study:**

Effect of Location of Tetanic Stimuli on Photopethysmogram During General Anesthesia

**\*Enter the study number or study alias**

PT1801

\* This field allows you to enter an abbreviated version of the Study Title to quickly identify this study.

### 2.0 Add Department(s)

**2.1 List departments and/or research programs associated with this study:**

Primary Dept?	Department Name		
	UCSF - 127037 - M_Anesthesia		

# Study Application (Version 1.0)

## 1.0 General Information

**\*Enter the full title of your study:**

Effect of Location of Tetanic Stimuli on Photopethysmogram During General Anesthesia

**\*Enter the study number or study alias**

PT1801

\* This field allows you to enter an abbreviated version of the Study Title to quickly identify this study.

## 2.0 Add Department(s)

**2.1 List departments and/or research programs associated with this study:**

Primary Dept?	Department Name		
	UCSF - 127037 - M_Anesthesia		

## 5.0 Initial Screening Questions - Updated 9/13

**(Note: You must answer every question on this page to proceed).**

**If you are converting to the new form, check questions 5.4, 5.6, 5.7, 5.8 and 5.10 before saving and continuing to the next section.**

**5.1 \* Application type:**

- Full Committee
- Expedited
- Exempt

**5.2 \* Risk level (Help Text updated 9/13):**

- Minimal risk  
 Greater than minimal risk

**5.3 \* Subject contact:**

- Yes (including phone, email or web contact)  
 No (limited to medical records review, biological specimen analysis, and/or data analysis)

**5.4 \* Funding (past or present):**

- Funded or will be funded (external sponsor, gift, program or specific internal or departmental funds)  
 Unfunded (no specific funds earmarked for this project)  
 Unfunded student project

**5.5 \* The Principal Investigator and/or one or more of the key study personnel has financial interests related to this study:**

- Yes  No

If **Yes**, the Conflict of Interest Advisory Committee (COIAC) office may contact you for additional information.

**5.6 \* This is an investigator-initiated study:**

- Yes  No

**5.7 \* This study ONLY involves retrospective records review and/or identifiable biospecimen analysis:**

- Yes  No

**5.8 \* This is a clinical trial:**

- Yes  No

**Clinical Trial Registration**

"NCT" number for this trial:

**5.9 \* This is a multicenter study:**

- Yes  No

**5.10 \* This application involves the study of unapproved or approved drugs, devices, biologics or in vitro diagnostics:**

- Yes  No

**5.11 \* This application involves a Humanitarian Use Device:**

- No  
 Yes, and it includes a research component  
 Yes, and it involves clinical care ONLY

**5.12 \* This study involves human stem cells (including iPS cells and adult stem cells), gametes or embryos:**

- No  
 Yes, and requires CHR and GESCR review  
 Yes, and requires GESCR review, but NOT CHR review

**5.13 \* This is a CIRB study (e.g. the NCI CIRB will be the IRB of record):**

- Yes  No

**5.14 \* This application includes a request to rely on another IRB (other than NCI CIRB):**

- Yes  No

Note: If this request is approved, the CHR will **NOT** review and approve this study. Another institution will be the IRB of record.

## 6.0 Expedited Review Categories

**6.1 \* If you think this study qualifies for expedited review, select the regulatory category(ies) that the research falls under:**

- Category 1: A very limited number of studies of approved drugs and devices  
 Category 2: Blood sampling  
 Category 3: Noninvasive specimen collection (e.g. buccal swabs, urine, hair and nail clippings, etc.)  
 Category 4: Noninvasive clinical procedures (e.g. physical sensors such as pulse oximeters, MRI, EKG, EEG, ultrasound, moderate exercise testing, etc.)  
 Category 5: Research involving materials (data, documents, records, or specimens) that were previously collected for either nonresearch or research purposes  
 Category 6: Use of recordings (voice, video, digital or image)  
 Category 7: Low risk behavioral research or research employing survey, interview, oral history, focus group, program evaluation, human factors evaluation, or quality assurance methodologies

**7.3 Check any research programs this study is associated with:**

- Cancer Center
- Center for AIDS Prevention Sciences (CAPS)
- Global Health Sciences
- Immune Tolerance Network (ITN)
- Neurosciences Clinical Research Unit (NCRU)
- Osher Center
- Positive Health Program

## 8.0 Study Design

**8.1 \* Study design (Help Text updated 9/13):**

This is a single center, clinical research study that plans to enroll 20 surgical patients undergoing general anesthesia.

**8.2 If this is a clinical trial, check the applicable phase(s) (Help Text updated 9/13):**

- Phase I
- Phase II
- Phase III
- Phase IV

## 9.0 Scientific Considerations

**9.1 Hypothesis (Help Text updated 9/13):**

This study has a hypothesis:

Yes  No

If yes, state the hypothesis or hypotheses:

During general anesthesia a tetanic stimulus-induced noxious stimulus will elicit a brief peripheral vasoconstrictive response which can be measured as a decrease in the AC component of a photoplethysmogram, and an increase in the DC component of the photoplethysmogram. The hypothesis of this study is that the location where the tetanic stimulus is applied has no effect on the peripheral vasoconstrictive response.

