**9.2 \* List the specific aims:**

To evaluate the effect of a noxious stimulus (tetanus) on the AC and DC components of a photoplethysmogram immediately before and after a tetanic stimulus applied to three different sites (ulnar nerve, thorax at mid axillary line, and over tibia).

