**9.3 Statistical analysis:**

Maximum changes in the AC and DC components of the photoplethysmogram will be determined during a 60 second period after a tetanic stimulus. Maximum changes in the AC and DC components will be compared to their respective baseline values using paired students t-test.  $p < 0.05$  will signify statistical significance. The maximum changes in the AC and DC components between the three different sites will be compared using ANOVA.

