## 10.0 Background

**10.1 Background:**

Noxious stimuli will induce a stress response in humans that activates the autonomic nervous system. This response can be observed in various ways such as peripheral vasoconstriction, increase in circulating catecholamine levels, increase in heart rate and blood pressure, etc. Numerous previous studies have used photoplethysmography (measures change in volume) to record these responses. Photoplethysmography is part of a commonly used noninvasive clinical monitoring system called pulse oximetry.

Heat, cold, and electrical current have been used as noxious stimuli in awake subjects. In surgical patients, tetanic stimulus has been established as a noninvasive, standardized noxious stimulus, that has been compared in intensity to the stimulus of a skin incision. Tetanic stimuli are routinely used during general anesthesia to monitor neuromuscular function.

A photoplethysmogram has two components, commonly referred to as AC and DC. The AC component is due to pulsatile changes in tissue volume (mainly arterial pulsation). The DC component is due to transmission of light by nonpulsatile tissues, including venous blood and nonpulsatile portions of arterial blood. Noxious stimuli-induced stress responses mediate peripheral vasoconstriction and will decrease the AC and increase the DC component of the photoplethysmogram. It is not known if the location of the tetanic stimulus has an effect on this stress response.

The aim of this study is to investigate the effect of a known noxious stimulus (tetanic stimulus), applied to three different sites, on both the AC and DC components of the photoplethysmogram in order to determine which component is best in detecting perioperative stress responses and if the location of the stimulus has an effect on the stress response.

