## 13.0 Procedures

**13.1 \* Procedures/Methods (Help Text updated 9/13)**

**For clinical research list all study procedures, test and treatments required for this study, including when and how often they will be performed. If there are no clinical procedures, describe the Methods:**

In addition to the clinically used pulse oximeter probe, two additional, noninvasive pulse oximeter probes (Masimo, Irvine CA, identical to the one used clinically) will be applied to both index fingers after induction of anesthesia. The probes are noninvasive and pose no known additional risk. Data from these probes will be collected using a laptop computer and ADC software, which is designed to collect photoplethysmography data from Masimo pulse oximeters. Data will be collected while patients are anesthetized. Data will be analyzed offline.

In addition to the pulse oximeter data, other available hemodynamic data will be collected electronically from GE hemodynamic monitors using another laptop computer and S/5 Collect software, which is commercially available for this purpose.

Tetanic stimulus: The study will use the same neuromuscular function monitor as is used clinically. Tetanic stimuli will be applied to the ulnar nerve, thorax at mid axillary line and over tibia. A 5 second, 100 Hz, 60 mA, stimulus will be used (similar to the one used clinically). Tetanus will be applied twice at each location (random order, minimum of 2 minutes apart).

Other than electronic data collection and addition of the two noninvasive pulse oximeter probes and periodic tetanic stimuli, this study will have no influence on surgery, anesthesia, or hemodynamic

monitoring, all of which are left to the discretion of the surgeon and anesthesiologist in charge of the patient.

In summary, the following data will be recorded:

1. Demographic data from APEX
2. Pulse oximeter data will be collected electronically using a laptop computer
3. Anesthetic agents will be recorded from APEX
4. Timing and location of the tetanic stimuli will be marked on the laptop computer.
5. All available electronic monitoring data (blood pressure, heart rate etc.) will be recorded electronically from the operating room hemodynamic monitors using a laptop computer.

If you have a procedure table, attach it to the submission with your other study documents.

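### Section 9.1 hypothesises that stimulus location has no effect, but the ANOVA in 9.3 can only contradict that hypothesis, never support it

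*Combined protocol and SAP*

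**What the plan says.** Section 9.1 has two parts. The first predicts a direction: after a tetanic stimulus the AC component falls and the DC component rises. The second concerns location: "The hypothesis of this study is that the location where the tetanic stimulus is applied has no effect on the peripheral vasoconstrictive response".

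Section 9.3 plans two analyses. The first does not compare sites: "Maximum changes in the AC and DC components will be compared to their respective baseline values using paired students t-test". The second does: "The maximum changes in the AC and DC components between the three different sites will be compared using ANOVA". The criterion is p < 0.05. It is stated before the ANOVA sentence and is taken here to apply to both tests.

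Elsewhere the location question is open. The title is "Effect of Location of Tetanic Stimuli on Photopethysmogram During General Anesthesia", and 10.1 asks "if the location of the stimulus has an effect on the stress response". The specific aim in 9.2 begins "To evaluate the effect of a noxious stimulus (tetanus) on the AC and DC components of a photoplethysmogram". It names the three sites and predicts nothing about them, but it states no comparison between sites either.

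On design, 13.1 says: "Tetanus will be applied twice at each location (random order, minimum of 2 minutes apart". Each patient therefore provides data at all three sites. Section 11.4 says 12 subjects are needed, based on a previous trial, and asks for up to 20 to allow for poor technical data quality. It gives no effect size, SD or power.

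**The concern.** A test for a difference starts from equality and looks for evidence against it. When the study's hypothesis is itself equality, the test can only count against that hypothesis. A non-significant ANOVA could mean that the sites produce similar responses, or that there were too few usable recordings or too much noise to see a difference. Nothing in the plan separates the two.

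Location is the title question, and 10.2 gives the added sites as the only difference from the preceding study. As written, no planned result can support the stated location hypothesis, and a reader of 9.1 could easily take a non-significant result as confirming it. The directional part of 9.1 is not affected, because the paired t-test can support it.

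**Working it through.** **1. The logic.** This step needs no assumed numbers.

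| ANOVA result | Bearing on 9.1 (no effect of location) | Bearing on 10.1 (does location matter?) |
|---|---|---|
| Significant | Refuted | Answered: yes |
| Non-significant | Not supported | Not answered without a margin or an interval |

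Sections 9.1 to 9.3 and 11.4 contain no margin, no equivalence test, no between-site interval and no rule for the second row.

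**2. The plan's own figure.** The 12 subjects in 11.4 cannot be reproduced, because no effect size, SD or power is given. Section 10.2 also says that no data exist on the effect of location, so nothing shows that the number was chosen for this question.

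**3. How ambiguous would a non-significant result be? (illustration)**

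Inputs from the documents: three sites, two stimuli per site (13.1), n = 12 or 20 (11.4), α = 0.05 (9.3).

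Assumptions:
- The ANOVA is repeated-measures with sphericity; 9.3 does not name the type.
- The unit is the SD of the within-patient difference between two sites with one stimulus per site. The residual variance is then 0.5.
- If the two stimuli are averaged, the SD is multiplied by f, between 1 (no gain) and 0.707 (largest possible gain).
- The largest gap between sites is d = 0.5 SD.

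The noncentrality is λ = n·S / (0.5·f²). S is the sum of squared deviations of the site means from their average: (2/3)d² = 0.1667 if one site is shifted, and d²/2 = 0.125 if the third site lies midway. For example, with n = 12, one site shifted and f = 1, λ = 12 × 0.1667 / 0.5 = 4.0. The probability of non-significance is that of a noncentral F with 2 and 2(n−1) df falling below its critical value (3.44 for n = 12, 3.24 for n = 20).

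| Pattern | f | λ, n = 12 | P(non-sig.) | λ, n = 20 | P(non-sig.) |
|---|---|---|---|---|---|
| One site shifted | 1 | 4.0 | 0.632 | 6.67 | 0.404 |
| Third site midway | 1 | 3.0 | 0.715 | 5.0 | 0.529 |
| One site shifted | 0.707 | 8.0 | 0.347 | 13.33 | 0.109 |
| Third site midway | 0.707 | 6.0 | 0.477 | 10.0 | 0.218 |

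The assumed gap matters. With one site shifted and f = 1, the probability is 84% (n = 12) or 75% (n = 20) at 0.3 SD, and 23% or 5% at 0.8 SD.

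**4. Precision of one site difference.** The Bonferroni-adjusted 95% half-width for three pairs is f·t(1 − 0.025/3, n−1)/√n.
- n = 12: 2.820/√12 = 0.814 SD at f = 1, and 0.576 SD at f = 0.707.
- n = 20: 2.625/√20 = 0.587 SD at f = 1, and 0.415 SD at f = 0.707.

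**5. What it would take to support no effect.** This was simulated with three sites, equal independent errors and a true difference of zero. Success means that all three pairwise 90% CIs lie inside the margin. Results are per component, AC or DC.

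| Quantity | f = 1 | f = 0.707 |
|---|---|---|
| Margin giving 80% power, n = 12 | 1.04 SD | 0.74 SD |
| Margin giving 80% power, n = 20 | 0.78 SD | 0.55 SD |
| Power at n = 20, margin 0.75 SD | 74% | 99% |
| Power at n = 20, margin 0.5 SD | 12% | 65% |
| Patients for 80% power, margin 0.75 SD | 22 | 12 |
| Patients for 80% power, margin 0.5 SD | 47 | 25 |

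**The case against.** The best defence is that 9.1 is a free-text answer on an ethics application and simply states the conventional null hypothesis, which is what an ANOVA tests. The title and 10.1 leave the question open, and 10.2 says there are no data on location, so there was little basis for predicting equivalence. On this reading the design and test agree and one sentence is loosely worded. The harm is also conditional: the plan does not say that a non-significant result will be read as support, and a significant one would answer 10.1 clearly.

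Much of this stands, and it is why the preferred remedy is mainly wording. It does not remove the problem. Section 9.1 does not call the sentence a null hypothesis. It presents it as the study's hypothesis, directly after a directional prediction that is meant to be supported. Even on the charitable reading, a non-significant ANOVA has no planned interpretation.

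It is also fair to say that the gap and margins in SD units are assumed and cannot be converted to AC or DC units from the documents. They illustrate the problem and do not establish it.

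**Conclusion.** The concern holds. As written, the plan can refute its location hypothesis but cannot support it, and it has no means of interpreting a non-significant result. That conclusion follows from 9.1 and 9.3 alone.

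Its practical size depends on a variability that the documents do not give. Under the stated assumptions and a largest gap of 0.5 SD, non-significance would occur 35% to 72% of the time with 12 patients and 11% to 53% with 20. These ranges hold for that gap only. The point should be fixed before analysis. Data collection and the test of the AC and DC response against baseline are not affected.

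**What to change.** **Preferred.**
- In 9.1, replace the location sentence with a question in line with the title and 10.1: whether the location of the tetanic stimulus affects the peripheral vasoconstrictive response.
- In 9.3, keep the overall test for a difference and specify it as within-patient, since 13.1 gives every patient all three sites.
- Add to 9.3: *The three pairwise within-patient site differences will be reported with multiplicity-adjusted 95% confidence intervals, for AC and for DC. A non-significant result will not be reported as no effect of location.*

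This costs a few sentences and some added reporting, with no extra patients or procedures. The drawback is that the location result may have to be called inconclusive.

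**Only if the no-effect claim is kept.** Fix and justify a margin in advance for AC and for DC. Conclude no relevant effect only if all three pairwise 90% CIs lie inside it. Otherwise report a difference if the overall test shows one, or an inconclusive result. This may cost patients: 80% power per component needs about 12 to 22 patients at a 0.75 SD margin and 25 to 47 at 0.5 SD, if the true difference is zero. Requiring AC and DC both to pass could need more.

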**9.2 \* List the specific aims:**

To evaluate the effect of a noxious stimulus (tetanus) on the AC and DC components of a photoplethysmogram immediately before and after a tetanic stimulus applied to three different sites (ulnar nerve, thorax at mid axillary line, and over tibia).

**9.3 Statistical analysis:**

Maximum changes in the AC and DC components of the photoplethysmogram will be determined during a 60 second period after a tetanic stimulus. Maximum changes in the AC and DC components will be compared to their respective baseline values using paired students t-test.  $p < 0.05$  will signify statistical significance. The maximum changes in the AC and DC components between the three different sites will be compared using ANOVA.

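### With probes on both index fingers and one stimulus site in a probed arm, must the plan name the finger that is analysed?

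*Combined protocol and SAP*

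**What the plan says.** Section 9.3 treats the recording as one signal: "Maximum changes in the AC and DC components of the photoplethysmogram will be determined during a 60 second period after a tetanic stimulus". The comparison of sites is then stated in one sentence: "The maximum changes in the AC and DC components between the three different sites will be compared using ANOVA". The section does not mention finger or side.

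Section 13.1 describes two study probes that "will be applied to both index fingers after induction of anesthesia". On the stimulus it says "Tetanic stimuli will be applied to the ulnar nerve, thorax at mid axillary line and over tibia", each train lasting 5 s, and "Tetanus will be applied twice at each location (random order, minimum of 2 minutes apart". The device is the one in routine use: "The study will use the same neuromuscular function monitor as is used clinically". Item 4 of the recorded-data list reads "Timing and location of the tetanic stimuli will be marked on the laptop computer".

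Section 9.2 frames the measurement as "immediately before and after a tetanic stimulus applied to three different sites". Section 9.1 puts the hypothesis in terms of peripheral vasoconstriction, with no effect of site expected. Section 10.1 speaks instead of the stress response. Section 11.4 asks for up to 20 patients where 12 are needed, to allow for poor signals.

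**The concern.** Two signals are collected and one endpoint is defined, with no rule linking them. An analyst could use the left finger, the right finger, the cleaner trace or an average. Side is not named among the recorded items, and nothing says that the two ulnar stimuli in a patient are on the same side.

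This touches the tested factor. A nerve stimulator at the ulnar nerve may move the hand or shift the probe; the same train at the thorax or tibia acts away from both probes. A disturbance confined to the stimulated hand would enter only the ulnar results, and only if that hand's finger is used. Random order does not remove it, because it follows site and not sequence. More patients do not remove it either, because a systematic bias is detected more often as n grows. The endpoint is a maximum, which one brief excursion can set. A false site difference, or a real one masked, would bear directly on the hypothesis that site does not matter.

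**Working it through.** **1. What the text fixes.** Both fingers are recorded; the ulnar nerve is the only site in a probed limb; the analysed finger is not named; location is marked for each stimulus, and side is not mentioned. All four points hold on reading 9.1 to 9.3, 10.1 and 13.1.

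**2. What the text says about timing.** The stimulus is a 5 s train. Sections 9.2 and 9.3 both place the measurement after it. On the ordinary reading the 60 s window opens when the train ends, so contraction during the train falls outside it. What remains is a disturbance that outlasts the train.

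**3. How large the effect would be.** The plan gives no artefact size, SD or typical response, and its figure of 12 patients cannot be reproduced because no effect size or power is stated. The following are assumptions: log-unit changes, within- and between-patient SD both 0.15, typical true peak 0.3 or 0.5, one value per patient and site, alpha 0.05, stimulated-hand finger used, all patients affected, repeated-measures ANOVA on three sites. Section 9.3 says only ANOVA.

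*Lasting shift b at the ulnar site.* The F test has 2 and 2(n−1) df and noncentrality λ = n × (b/0.15)² × 2/3. With b = 0.10:
- n=12: λ = 12 × 0.444 × 0.667 = 3.56, rejection 33%.
- n=20: λ = 5.93, rejection 54%.
- Averaging two fingers halves b: λ = 0.89 and 1.48, rejection 11% and about 16%.
- If only half the patients are affected, simulation gives 11% and 16%.

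*Brief artefact A.* It matters only where it exceeds the true peak, so the observed value is max(true, A). With s = √(0.15² + 0.15²) = 0.212 and d = (A − peak)/s, the bias is s × [φ(d) + d × Φ(d)]. False site effects come from 40,000 simulated trials per cell:

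| Peak | A | Bias | n=12 | n=20 |
|---|---|---|---|---|
| 0.5 | 0.10 | 0.002 | 5% | 5% |
| 0.5 | 0.20 | 0.008 | 5% | 5% |
| 0.5 | 0.30 | 0.020 | 6% | 7% |
| 0.3 | 0.10 | 0.020 | 6% | 7% |
| 0.3 | 0.20 | 0.044 | 10% | 15% |
| 0.3 | 0.30 | 0.085 | 27% | 46% |

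For example, peak 0.3 and A = 0.30 give d = 0 and bias 0.212 × 0.399 = 0.085.

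*Masking.* If the ulnar response is truly weaker by 0.15 (changes floored at 0), a brief 0.10 artefact lowers power from 60% / 86% to 37% / 62% (n=12 / 20) at peak 0.3, but only from 65% / 89% to 61% / 86% at peak 0.5.

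*Ordinary one-way ANOVA.* The lasting 0.10 shift gives 9% / 19%. Brief artefacts give under 1% at peak 0.5 and at most about 8% / 17% at peak 0.3. These lower rates reflect that test's conservatism with paired data; the bias is the same.

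**4. Whether the data could reveal a disturbance.** With both fingers recorded, the between-finger difference at the ulnar site has a 95% half-width of 0.043 / 0.031 (n=12 / 20) at an assumed between-finger correlation of 0.9, and 0.074 / 0.054 at 0.7. A mean shift of 0.10 would be visible, provided the side stimulated is known.

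**5. Which question each finger answers.** The finger opposite the ulnar stimulus measures the remote response, close to the wording of 10.1. A stronger vasoconstriction in the stimulated arm is a genuine location effect under 9.1 and would leave the primary analysis if the opposite finger were made primary.

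**The case for a change.** The best case for a change is that it costs a few sentences and one recorded item. Naming the finger opposite the ulnar stimulus keeps false site effects at 5% if that hand is undisturbed, and it removes the freedom to pick a finger after seeing the data. The price in precision is small: power for a 0.15 effect is 65% / 89% (n=12 / 20) with one finger, against 68% / 91% or 73% / 94% with two, at assumed correlations of 0.9 and 0.7. A lasting probe shift would survive any reading of the window, and a side left unmarked could not be recovered from the traces with certainty.

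Part of this stands. The finger is unnamed, the choice is open, and side would be useful to note. But the argument shows only that a rule would be tidy. Its premise, a disturbance of the stimulated hand that reaches the maximum, is not in the documents; the clinical stimulator shows what device is used and no more. Marking location can naturally include side, and under 13.8 one investigator collects the data. The proposed rule is also not neutral: it moves a local response, which 9.1 counts, to secondary status. Naming the stimulated-hand finger instead would readmit the supposed artefact.

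**Conclusion.** No change to the plan is needed. The missing rule is a detail that an analyst can fill sensibly, since both fingers are recorded and can be reported side by side, and the choice between them is a fair trade-off between the local and the remote response. Marking side along with location, and reading the 60 s as starting when the train ends, are ordinary good practice within the present text.

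The possible size runs from nothing (5% to 7% false site effects for a brief artefact at peak 0.5) to substantial (33% / 54% at n=12 / 20 for a lasting 0.10 shift in every patient). All these figures rest on assumed SDs, peaks, artefact sizes and proportions affected, and on repeated-measures ANOVA. One log-unit scale is used for both AC and DC, and nothing in the documents shows that it suits DC. The figures show what a disturbance could do and are not evidence that one occurs. Evidence of a lasting disturbance of the stimulated hand would alter this conclusion.

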**11.4 Explain how and why the number of subjects was chosen (Help Text updated 9/13):**

Based on the previously completed trial, 12 subjects will be needed. I'm requesting to study up to 20 patients in case there will be patients with poor technical data quality.

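### The three-site comparison should name patient as a factor and fix one value per patient per site; the plan says only ANOVA

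*Combined protocol and SAP*

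**What the plan says.** Section 9.1 states the hypothesis that "the location where the tetanic stimulus is applied has no effect on the peripheral vasoconstrictive response". Section 9.3 tests it in one sentence: "The maximum changes in the AC and DC components between the three different sites will be compared using ANOVA". The same section is explicit about pairing for a different comparison: "Maximum changes in the AC and DC components will be compared to their respective baseline values using paired students t-test".

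Section 13.1 describes a within-patient design: "Tetanus will be applied twice at each location (random order, minimum of 2 minutes apart". The two study probes "will be applied to both index fingers after induction of anesthesia". It does not say which arm receives the ulnar stimulus.

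Section 11.4 gives the sample size: "Based on the previously completed trial, 12 subjects will be needed". It anticipates that some patients will have poor data and allows for this by "requesting to study up to 20 patients in case there will be patients with poor technical data quality".

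No section mentions repeated measures, a patient or block term, a mixed model, or a rule for combining the two stimuli and two fingers at a site.

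**The concern.** Each patient serves as his or her own control for location. That removes differences between patients from the site comparison, but only if the analysis uses it. ANOVA without further description covers at least three analyses of these data:

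- repeated-measures ANOVA, with patient as a factor;
- ordinary one-way ANOVA on one mean per patient per site;
- ordinary one-way ANOVA on every reading.

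Their error rates differ widely. The direction matters because the hypothesis is one of no effect: a test that loses power tends to return the result that the study expects. If the choice is left until the data are in hand, it can also be influenced by them.

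**Working it through.** **Counts (section 13.1).** 3 sites × 2 stimuli = 6 stimuli per patient, and × 2 fingers = 12 readings per component. With 12 patients that is 144 readings but only 36 patient-site means; with 20 patients, 240 and 60.

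**The plan's own figure.** The 12 patients cannot be reproduced. Section 11.4 gives no effect size, standard deviation, power or within-patient correlation.

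**Assumptions (none from the documents).** Normal data; variance 1 for a single finger reading, split as patient P = 0.3, patient-by-site PS = 0.2, stimulus S = 0.4, finger F = 0.1; one site shifted by 0.5 SD; level 0.05. The two fingers are treated as exchangeable.

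**Error variance of a patient-site mean.**
- Patient as a factor: E = PS + S/2 + F/4 = 0.2 + 0.2 + 0.025 = 0.425.
- Patient left out: P + E = 0.3 + 0.425 = 0.725.

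**Repeated measures.** The sum of squared site effects is 0.5² × 2/3 = 0.1667, and the noncentrality is n × 0.1667 / E.
- n = 12: 12 × 0.1667 / 0.425 = 4.71 on F(2, 22), power 42%.
- n = 20: 20 × 0.1667 / 0.425 = 7.84 on F(2, 38), power 67%.

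**Ordinary ANOVA on the same means.** With no site effect the site mean square has expectation 0.425 and the residual 0.725. The F ratio therefore centres near 0.425 / 0.725 = 0.59 instead of 1. By simulation (at least 20,000 trials per cell), type I error is about 1% at n = 12, and power is 20% at n = 12 and 39% at n = 20.

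**Ordinary ANOVA on all readings as independent rows, n = 12.** The expected site mean square is 4 × 0.425 = 1.70. The expected residual is (48 − 4 × 0.725) / 47 = 0.96. The ratio is 1.77, and simulated type I error is about 19%. With patient variance dominant (0.8/0.05/0.1/0.05), E = 0.05 + 0.05 + 0.0125 = 0.1125, the site mean square is 0.45 against a residual of (48 − 4 × 0.9125) / 47 = 0.94, and type I error is about 0.9%. The direction is not fixed.

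**Sensitivity, n = 12.** The first row covers 16 assumed splits, all with patient variance of at least 0.1, so its ranges depend on that choice.

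| Split | Power, ordinary on means | Power, repeated measures | Type I, all rows |
|---|---|---|---|
| 16 splits | 4–31% | 31–99% | 0.1–33% |
| Patient variance 0.05 (0.05/0.2/0.55/0.2) | 32% | 35% | 25% |
| Patient variance 0 (0/0.2/0.6/0.2) | 35% | 34% | 26% |

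**What blocking does not do.** In the 0.3/0.2/0.4/0.1 split at n = 12, 100 − 42 = 58% of trials with a real 0.5 SD shift would still be non-significant. The 95% confidence interval for a pairwise site difference has half-width 2.201 × √(2 × 0.425 / 12) = 0.59 SD at n = 12 and 2.093 × √(2 × 0.425 / 20) = 0.43 SD at n = 20.

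**A caution for mixed models.** With 12 patients and complete data, a large-sample Wald chi-square test of site rejects when F exceeds 5.99 / 2 = 2.996. P[F(2, 22) > 2.996] = 0.071, so the true level is about 7%.

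**The case against.** The strongest reply is that this is silence and not a wrong method. The text is a short field in an ethics application, and an investigator who stimulates every patient at every site may well mean repeated-measures ANOVA. That stands. It still leaves open how two stimuli and two fingers become one value, and writing it down costs a sentence.

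Second, every figure rests on invented variances. That also stands: the figures show what could be at stake, not what will happen. The gap in the text does not depend on them.

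Third, section 11.4 already allows for poor data. It does, for whole patients, by enrolling up to 20 when 12 are needed. It does not say how the readings within a usable patient are combined, which is the point here.

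Fourth, averaging the fingers is only one choice, and it may mix the arm receiving the ulnar stimulus with the other arm. That is fair, and a single prespecified finger would serve equally well.

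A reader might infer that the planned analysis is wrong, that type I error will be inflated, or that 12 patients are too few. The documents support none of these. They do not say that an ordinary ANOVA will be run or that readings will be treated as independent, and they give no inputs against which to judge the 12.

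**Conclusion.** The point holds as a gap in specification with a clearly better way to fill it. Section 9.3 does not commit to using the within-patient structure that section 13.1 creates. If an ordinary ANOVA on patient-site means were run, it would be conservative and lose power: roughly half of it at 12 patients in the illustrative split (20% against 42%). The loss would lean towards the study's own hypothesis. If all readings were entered as independent rows, type I error could fall below 5% or rise well above it. These sizes rest on assumed variance components, a 0.5 SD shift, normal data and exchangeable fingers. The power advantage of blocking disappears as patient variance approaches zero. This is a free improvement.

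**What to change.** Add to section 9.3:

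1. Reduce the data to one value per patient per site for AC and for DC, by a prespecified rule applied identically at all sites. Use either the mean over the usable readings from both stimuli and both fingers, or one prespecified finger with its side relative to the ulnar stimulus stated. Define usable in advance and without regard to site.
2. Compare sites separately for AC and DC with patient as a blocking factor, by repeated-measures ANOVA. If a patient lacks a site, use a linear model with patient as a block, or a mixed model with a small-sample F test such as Kenward-Roger, and not a large-sample Wald test.
3. Report the three pairwise site differences for each component with confidence intervals, and state whether they are adjusted for multiplicity. A non-significant ANOVA does not by itself show that location has no effect.
4. Use the same patient-level values in the paired t-tests, so that n is the number of patients.

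The cost is a few sentences. No new data, patients or procedures are needed, since section 13.1 already provides that "Timing and location of the tetanic stimuli will be marked on the laptop computer". The only statistical price is about one point of power (34% against 35% in the case worked above) if patients do not differ at all.
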